#### **10.4.2. Fistula Abandonment**

The index AV fistula will be classified as abandoned if any of the following conditions are met:

- For subjects undergoing hemodialysis during the course of study participation:
  - The fistula was never used for 2-needle dialysis during the study period (fistula will be considered abandoned on the day of creation);
  - The fistula can no longer be used for 2-needle dialysis and there is no expectation of future use
  - Placement of a new vascular access for hemodialysis

- The fistula undergoes surgical revision of the anastomosis.
- For subjects who were not on hemodialysis on day of enrollment and who never initiated hemodialysis during the course of study participation:
  - The fistula was designated as being abandoned by the investigator. The investigator's decision to abandon the fistula may be based on:
    - The results of a clinical evaluation of the fistula
    - In some instances, at the discretion of the investigator, the decision to abandon the fistula may be based on the results of an imaging study (ultrasound or angiogram)
  - The fistula undergoes surgical revision of the anastomosis
  - Placement of a new vascular access for hemodialysis.

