#### **10.4.3. Censored Events**

Subjects experiencing censoring events before an endpoint is observed will be included in the statistical analysis up to the time at which they achieve the censoring event. They will be censored (excluded) from the analysis after that time point. These censoring rules apply to all efficacy endpoints.

Censored events include:

- Death
- Renal transplantation
- Transfer to peritoneal dialysis

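### Going to peritoneal dialysis is censored whatever its reason and is not an abandonment criterion, so a failed fistula in a subject who never started hemodialysis can go uncounted in secondary patency

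*Combined protocol and SAP*

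**What the plan says.** Section 10.4.3 names three censoring events: death, renal transplantation and "Transfer to peritoneal dialysis". The rule covers "Subjects experiencing censoring events before an endpoint is observed", and of these subjects it says "They will be censored (excluded) from the analysis after that time point". On scope it adds: "These censoring rules apply to all efficacy endpoints". It sets no condition on the reason for the move to PD or on the state of the fistula at that time, and no order of precedence when a failure and a transfer fall close together.

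Section 10.2.3 makes access abandonment the only event for secondary patency. Section 10.4.2 defines abandonment in two branches. In the branch for subjects undergoing hemodialysis, a fistula never used with two needles counts as abandoned from the day of creation, and one that can no longer be used and is not expected to be used again also counts. The other branch applies "For subjects who were not on hemodialysis on day of enrollment and who never initiated hemodialysis during the course of study participation". It gives three routes:

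- "The fistula was designated as being abandoned by the investigator", on clinical evaluation or, at the investigator's discretion, imaging
- "The fistula undergoes surgical revision of the anastomosis"
- "Placement of a new vascular access for hemodialysis"

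Section 13.3.4 analyses time-to-event secondary endpoints by stratified log-rank test. It describes no competing-risk or sensitivity analysis.

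**The concern.** A fistula that does not mature is a plausible reason for a patient not yet on hemodialysis to go to PD. If that happens before anyone designates the fistula as abandoned, the rules as written remove the subject as a patent fistula at the point of failure. The log-rank test and Kaplan-Meier estimate treat censored subjects as having the same outlook as those still followed, and these subjects may not.

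Three results are exposed. Secondary patency, a secondary endpoint in the step-down sequence, loses events. The re-intervention rate loses the one intervention that Section 10.2.4 assigns to each abandonment. Time to first dialysis (TTFD), a tertiary endpoint, censors a hemodialysis subject who moves to PD because the fistula was unusable, as if that fistula could still have reached first dialysis.

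**Working it through.** **The plan's own figure.** Power is stated only for FSD6 (Section 13.2): 45% against 65%, N = 200, two-sided 0.05, about 82%. Pooled-variance z-test with 100 per arm and mean proportion 0.55: Φ[(0.20 − 1.96 × √(2 × 0.55 × 0.45/100)) / √(0.45 × 0.55/100 + 0.65 × 0.35/100)] = Φ[(0.20 − 0.1379)/0.0689] = Φ(0.90) = 81.6%. It reproduces, but has no bearing on this point.

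**The rules applied to four subjects who go to PD.**

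| Subject | Status in secondary patency |
|---|---|
| On hemodialysis, fistula never used with two needles | Event on day 0 (10.4.2, hemodialysis branch) |
| Never on hemodialysis, abandonment designated before PD | Event at designation |
| Never on hemodialysis, fistula failed, no qualifying event before PD, move read as a transfer | Censored as patent |
| Same, direct PD start not read as a transfer | At risk as patent, with no event from the PD start |

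The first and third subjects may have equally unusable fistulas but get opposite event status. A designation made on or after the transfer date also points to censoring, because no tie rule is given.

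**Size, for illustration only.** The documents give no patency rate and no PD rate. Assumptions:

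- 110 per arm (about 220 randomised 1:1, Section 7.1).
- Exponential abandonment, 12-month risk 40% control and 25% SeCI (assumed).
- Half of each arm never on hemodialysis. This is near the ceiling: at least 100 of about 200 evaluable subjects must be on hemodialysis at the index procedure (Section 7.1), and others will start during the year.
- A share f of failures in that half censored at the time of failure (assumed).

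Hazard ratio (HR) = ln(0.75)/ln(0.60) = 0.2877/0.5108 = 0.563, so |ln HR| = 0.574. Events with nothing lost = 110 × (0.40 + 0.25) = 71.5. With share f, observed events = 71.5 × (1 − f/2), estimated 12-month abandonment = 1 − (1 − q)^(1 − f/2), where q is the true risk, and Schoenfeld power = Φ(√(events/4) × |ln HR| − 1.96).

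| f, both arms | Events | Lost | Estimated abandonment, control / SeCI | Power |
|---|---|---|---|---|
| 0 | 71.5 | 0 | 40% / 25% | 68% |
| 10% | 67.9 | 3.6 | 38% / 24% | 66% |
| 20% | 64.4 | 7.2 | 37% / 23% | 63% |
| 30% | 60.8 | 10.7 | 35% / 22% | 61% |

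With equal shares the hazard ratio stays at 0.563. With unequal shares it becomes 0.563 × (1 − f_SeCI/2)/(1 − f_control/2):

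- 30% control, 10% SeCI: 0.563 × 0.95/0.85 = 0.63
- 10% control, 30% SeCI: 0.563 × 0.85/0.95 = 0.50

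The first dilutes the effect and the second inflates it.

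**The case against.** The strongest reply is that the failure will normally be recorded first. Censoring applies only before the endpoint is observed, designation is the natural route for a fistula that does not mature, and the visits look for it: access assessments at 2, 3, 6, 9 and 12 months, and duplex ultrasound at 3, 6 and 12 months for fistulas not in use (Sections 7.3.9 to 7.3.13). This stands in part. A reader might infer that every fistula failure followed by PD is lost, and the documents do not support that: a failure recorded before the move is an event. But designation is a judgement with no set timing. Section 9.2.3 bars a person who knows the assignment only from deciding abandonment exclusively, so timing could differ by arm.

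Second, a subject who starts directly on PD has arguably not transferred. On that reading the subject is not censored but stays at risk as patent, and a later designation could still count. The gap in Section 10.4.2 remains, because the move to PD itself supplies no event.

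Third, Section 13.1 says the SAP holds the derivation algorithms. No separate SAP text beyond Section 13 was available, so a precedence rule there cannot be excluded.

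Fourth, the effect is small and its size is assumed. That is fair: power falls by 2 to 7 points in the equal-share cases, and with no moves to PD there is no effect.

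**Conclusion.** The point holds as a gap in the event definition. Followed literally, Sections 10.4.2 and 10.4.3 give the wrong secondary-patency status to a subject who never started hemodialysis, whose fistula has failed, and who goes to PD with no qualifying event recorded first. The likely consequence is a modest loss of events and overstated secondary patency. The figures rest on assumed abandonment risks, assumed shares and a near-ceiling proportion never on hemodialysis.

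Three further inferences should be resisted.

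- That the loss falls mainly on control: the documents give no PD rate by arm, and the bias can favour either side.
- That the plan declares this censoring non-informative: it does not say so; the assumption comes with the log-rank method.
- That only time-to-event endpoints are touched: Section 10.4.3 covers all efficacy endpoints, although it does not explain what exclusion after a time point means in the logistic regression for FSD6.

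The TTFD part carries less weight. That endpoint is tertiary, and Section 13.3.4 specifies the log-rank test only for secondary endpoints.

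**What to change.** 1. In Section 10.4.2, in the branch for subjects who never start hemodialysis, state that going to PD, by transfer or direct start, with an index fistula thrombosed or judged non-functional at or before that date is an abandonment dated no later than the PD start. The judgement is made blinded to treatment and before database lock.
2. In Section 10.4.3, limit PD censoring to subjects whose index fistula was still functional. Abandonment takes precedence when both fall on the same date, or when the designation follows the transfer for a failure already present.
3. For TTFD, treat a subject who moves to PD with an unusable fistula as not having reached first dialysis through the end of follow-up.
4. Add a sensitivity analysis of secondary patency that counts every move to PD as a failure.

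The rule rests on fistula status at the move, because the motive for choosing PD is harder to establish than whether the fistula worked. The cost is a few sentences, one eCRF field and a blinded judgement of fistula status. That judgement keeps some subjectivity, which item 4 helps to bound.

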## **11. ASSESSMENT OF SAFETY**

Safety evaluations will be based on treatment emergent adverse events (TEAEs) up to the 2 month visit and vascular access events reported during the study. Treatment emergent is defined as any adverse event that emerges after the subject is enrolled (run-in and randomized) in the study. The run-in subjects' adverse events will be included in the safety evaluation. Vascular access events include access dysfunction, thrombosis, access-related hand ischemia, infiltration requiring a rest period, fistula-related bleeding, infection, problems with wound healing, aneurysm, pseudoaneurysm, and all interventional procedures performed on the study fistula. During follow-up, after the 2 month visit, the following will be reported and recorded: vascular access events, concomitant medications and therapies associated with vascular access, serious adverse events (SAEs) and AEs reported during an SAE. At each follow-up visit up to the 2 month visit, AEs and concomitant medications will be recorded. Changes in comparison to baseline and the 2 month visit that are considered to be clinically significant will be reported as AEs.

## **12. ADVERSE AND SERIOUS ADVERSE EVENTS**

### **12.1. Adverse Event Definition**

An adverse event (AE) is any untoward medical occurrence in a subject participating in a clinical study. It includes:

- Any unfavorable and unintended sign, symptom or disease temporally associated with the use of the investigational product, whether or not considered to be caused by the investigational product
- AEs commonly observed and anticipated based on the pharmacological effect of the investigational product
- Any laboratory abnormality, vital sign, or finding from physical examination assessed as clinically significant by the investigator (note: findings from assessments and examinations done during screening are not AEs, but are recorded as medical history)
- Accidental injuries, reasons for any change in medication (drug and/or dose), reasons for any medical, nursing or pharmacy consultation, or reasons for admission to hospital or surgical procedures
- Overdoses and medication errors with and without clinical consequences.

### **12.2. Collection and Recording of Adverse Events**

#### **12.2.1. Collection of Adverse Events**

The investigator must monitor the condition of the subject throughout the study from the time of obtaining informed consent until the last visit. Findings from assessments and examinations done during screening are not AEs, but are recorded as medical history. Safety evaluations will be based on treatment emergent adverse events (TEAEs) up to the 2 month visit and vascular access events reported during the study. Vascular access events include access dysfunction, thrombosis, access-related hand ischemia, infiltration requiring a rest period, fistula-related bleeding, infection, problems with wound healing, aneurysm, pseudoaneurysm, and all interventional procedures performed on the study fistula. Treatment emergent is defined as any adverse event that emerges after the subject is enrolled (run-in and randomized) in the study. Following the 2 month visit the following will be reported and recorded: vascular access events, concomitant medications and therapies associated with vascular access, serious adverse events (SAEs) and AEs reported during an SAE.

The sources of AEs may cover:

- The subject's response to questions about his/her health (a standard non-leading question such as "How have you been feeling since your last visit?" is asked at each visit)

- Symptoms spontaneously reported by the subject
- Investigations and examinations where the findings are assessed by the investigator to be clinically significant changes or abnormalities
- Other information relating to the subject's health becoming known to the investigator (e.g., hospitalization, etc.)

### **12.2.2. Recording of Adverse Events**

The investigator must record all AEs in the Adverse Event Log provided in each subject's eCRF from the time of enrollment up to the 2 month visit. Following the 2 month visit through end of study, reporting requirements change to only reportable AEs (vascular access events and SAEs). Information to be recorded includes:

- Adverse event
- Date of onset
- Severity
- Causal relationship to investigational product
- Action taken to investigational product
- Other action taken
- Date of outcome
- Outcome
- Seriousness

Each of the items in the Adverse Event Log is described in detail in the following sections.

#### **Adverse Event**

Adverse events must be recorded as diagnoses, if available. If not, separate signs and symptoms should be recorded. One diagnosis/symptom should be entered per record.

If a subject suffers from the same AE more than once and the subject recovers in between the events, the AEs should be recorded separately. If an AE changes in intensity, a worst-case approach should be used when recording the event, i.e., the highest intensity and the longest duration of the event.

Note the following: A procedure is not an AE; the reason for conducting the procedure is. Hospitalization is not an AE; the reason for hospitalization is. Death is not an AE, but the cause of death is (an exception is sudden death of unknown cause or any death of unknown cause, which is an SAE).

#### **Date of Onset**

The date of onset is the date when the first sign(s) or symptom(s) were first noted. If the AE is an abnormal clinically significant laboratory test or outcome of an examination, the onset date is the date the sample was taken or the examination was performed.

## Severity

The following 3-point rating scale must be used for rating of the intensity of each adverse event:

- Mild: Awareness of signs or symptoms, but no disruption of usual activity
- Moderate: Event sufficient to affect usual activity (disturbing)
- Severe: Inability to work or perform usual activities (unacceptable)

## Causal Relationship to Investigational Product

The following 4-point scale must be used for rating the causal relationship of the AE to the investigational product:

- **Unrelated:** Clearly and incontrovertibly due only to extraneous causes, and does not meet criteria listed under unlikely, possible or probable.
- **Unlikely:** Does not follow a reasonable temporal sequence from administration. May have been produced by the subject's clinical state, environmental factors, or other therapies administered.
- **Possible:** Follows a reasonable temporal sequence from administration. May have been produced by the subject's clinical state, environmental factors, or other therapies administered.
- **Probable:** Clear-cut temporal association with improvement on cessation of investigational product (explanted). Follows a known pattern of response to the investigational product.
- **Direct:** Clear relationship to the investigational product. Event follows a known pattern of response to the investigational product.

Adverse events with the causality assessed as unrelated or unlikely are categorized as not related to investigational product.

Adverse events with the causality assessed as possible, probable, or direct are categorized as related to investigational product and are called adverse drug reactions (ADRs).

## Action Taken to Investigational Product

The action taken to the investigational product in response to an AE must be classified as one of the following:

- None
- Access Intervention
- Concomitant Medication
- Transfusion Performed
- Emergency Room Visit
- IP Explanted
- Unknown

- Other

### **Other Action Taken**

Adverse events requiring therapy must be treated with recognized standards of medical care to protect the health and well-being of the subject. Appropriate resuscitation equipment and medicines must be available to ensure the best possible treatment of an emergency situation.

If medication is administered to treat the AE, this medication must be entered in the Concomitant Medication Log.

### **Date of Outcome**

The date the subject recovered or died.

### **Outcome**

The outcome of an AE must be classified as one of the following:

- Recovered (fully recovered or the condition has returned to the level observed at initiation of study treatment)
- Recovered with sequelae (resulted in persistent or significant disability/incapacity)
- Recovering (condition still exists and is improving)
- Not recovered (condition still exists, has not improved; condition is irreversible, recovery/resolution not possible)
- Unknown
- Fatal

#### **12.2.3. Pregnancy and Pregnancy Outcome**

Every effort must be made to avoid pregnancy during the study. If a pregnancy does occur, the sponsor must be informed within 3 calendar days, using an SAE Report Form provided by the sponsor and/or designee. Note that pregnancy itself is not an SAE. Contact details for the follow-up on the pregnancy should be provided. The mother and the fetus must be followed up at least until the birth of the infant and one month after the birth of the infant. In general, the follow-up will include the course, duration and the outcome of the pregnancy and the health of the infant. If a pregnancy results in an abnormal outcome, which the Investigator and/or sponsor consider to be related to the investigational product, this outcome will be treated as an expedited report (See Section [12.3.2.2](#)).

## 12.3. Serious Adverse Events

### 12.3.1. Serious Adverse Event Definition

An event is defined a serious adverse event if it:	Guidance
results in death	Any event resulting in a fatal outcome must be fully documented and reported, including deaths occurring within four weeks after the treatment ends and irrespective of the causal relationship to the investigational product. The death of a subject enrolled in a study is per se not an event, but an outcome.
is life-threatening	The term “life-threatening” refers to an AE in which the subject was at immediate risk of death at the time of the event. It does not refer to an event, which may have caused death if it were more severe.
requires in-patient hospitalization or prolongation of existing hospitalization	The term “hospitalization” means that the subject was admitted to hospital or that existing hospitalization was extended as a result of an event. Hospitalization describes a period of at least 24 hours. Over-night stay for observation, stay at emergency room or treatment on an out-patient basis do not constitute a hospitalization. However, medical judgment must always be exercised and, when in doubt, the case should be considered serious (i.e., if the case fulfills the criterion for a medically important event). Hospitalizations for administrative or social purposes do not constitute an SAE. Hospital admissions and/or surgical operations planned before study inclusion are not considered AEs, if the illness or disease existed before the subject was enrolled in the study, provided that the condition did not deteriorate during the study.
results in persistent or significant disability/incapacity	Disability/incapacity means a substantial disruption of a person’s ability to conduct normal life functions. If in doubt, the decision should be left to medical judgment by the investigator.
is a congenital anomaly/birth defect	Congenital anomaly/birth defect observed in any offspring of the subject conceived during treatment with the IP.
is an important medical event	Important medical events are events that may not be immediately life-threatening or result in death or hospitalization but may jeopardize the subject or may require intervention to prevent one of the other outcomes listed in the definition above. Examples of important medical events include AEs that suggest a significant hazard, contraindication or precaution, occurrence of malignancy or development of drug dependency or drug abuse. Medical and scientific judgment should be exercised in deciding whether events qualify as medically important.  Important medical events include any suspected transmission of an infectious agent via a medicinal product. Any organism virus or infectious particle (e.g., prion protein transmitting Transmissible Spongiform Encephalopathy), pathogenic or non-pathogenic, is considered an infectious agent. A transmission of an infectious agent may be suspected from clinical symptoms or laboratory findings indicating an infection in a subject exposed to a medicinal product.

An AE caused by an overdose or medication error is considered serious if a criterion listed in the definitions above is fulfilled.

### **12.3.2. Collection, Recording and Reporting of Serious Adverse Events**

#### **12.3.2.1. SAE Reporting by the Investigator**

The investigator and/or designee must begin reporting all Serious Adverse Events starting the day of enrollment. Events that meet the SAE criteria listed prior to enrollment, should be documented in Medical History. The investigator is responsible to review these events and ensure the subject remains eligible for participation prior to proceeding with enrollment should the event occur in the 45 day screening period. All SAEs must be reported **immediately** to the sponsor and/or designee as soon as it becomes known and not later than within 24 hours of their knowledge of the occurrence of an SAE.

The investigator and/or designee is responsible for submitting the completed SAE Report Form with the fullest possible details **within 3 calendar days** of his/her knowledge of the SAE.

Additional information relevant to the SAE such as hospital records, results from investigations, e.g., laboratory parameters, invasive procedures, scans and x-rays, and autopsy results can be uploaded in the eCRF or provided to the sponsor and/or designee using the contact details in **Table 1**. In any case, the investigator and/or designee, upon request from the sponsor and/or designee, must supply this information. On any copies provided, details such as subject's name, address, and hospital ID number must be concealed and instead the subject number should be provided.

The investigator and/or designee will supply the sponsor and/or designee and the IRB with any additional requested information such as results of post-mortem examinations and hospital records.

